• BNT162b2 Bivalent 30 µg + BNT162b4 15 µg or • BNT162b2 Bivalent 30 µg	• BNT162b2 Monovalent (OMI XBB.1.5) 30 µg + BNT162b4 15 µg	45 15	3:1
Cohort 4a – Sentinel subjects aged 18-55 yrs	Cohort 4a – Sentinel subjects aged 18-55 yrs		
• BNT162b2 Bivalent 30 µg + BNT162b4 30 µg or • BNT162b2 Bivalent 30 µg	• BNT162b2 Monovalent (OMI XBB.1.5) 30 µg + BNT162b4 30 µg	6 2	3:1
Cohort 4a – Expansion subjects aged 18-55 yrs	Cohort 4a – Expansion subjects aged 18-55 yrs		
• BNT162b2 Bivalent 30 µg + BNT162b4 30 µg or • BNT162b2 Bivalent 30 µg (one dose)	• BNT162b2 Monovalent (OMI XBB.1.5) 30 µg + BNT162b4 30 µg	39 13	3:1
Cohort 4b – Subjects aged >55 yrs^b	Cohort 4b – Subjects aged >55 yrs^b		
• BNT162b2 Bivalent 30 µg + BNT162b4 30 µg or • BNT162b2 Bivalent 30 µg (one dose)	• BNT162b2 Monovalent (OMI XBB.1.5) 30 µg + BNT162b4 30 µg	45 15	3:1
Cohort 5 – Subjects aged 18-55 yrs	Cohort 5 – Subjects aged 18-55 yrs		
• BNT162b4 30 µg	• BNT162b4 30 µg	20	Not applicable

a) If the subject consents to a second dose of IMP as implemented using protocol version 5.0.

b) In Cohorts 3b and 4b, the age group distribution enrolled will be ~60% of subjects aged ≥65 yrs and ~40% of subjects aged >55 to <65 yrs.

c) Dose 1 is given observer-blind for Cohorts 1 to 4 and open-label for Cohort 5.

d) Dose 2 is given open-label for Cohorts 1 to 5. For Cohorts 1 to 4, Dose 2 is at 6 to 7 months post-Dose 1. For Cohort 5, Dose 2 is at 2 months post-Dose 1.

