1.3 Schedule of activities

The SoAs provide an overview of the trial visits and procedures. The investigator may conduct unplanned visits in addition to those listed in the SoAs, in order to conduct evaluations or assessments required to protect the wellbeing of the trial subjects.

If, for any reason, subjects are permanently discontinued from the trial before completing all scheduled visits, if possible trial subjects should complete all assessments planned for the Early Termination Visit.

For the SoA for Cohort 5, see Section 13.5.

For Cohorts 1 to 4, Visit 0 to Visit 6 apply for all subjects, Visit 7 to Visit 11 only apply for subjects who consent to a second dose of IMP after issue of protocol version 5.0.

Table 3: Schedule of activities – Cohorts 1 to 4

Activity	Visit 0 (V0)	V1	V1	V2 °	V3	V4	V5	V6 P	V7 P	V8	V9	V10	V11	Early term. Visit	Unscheduled ¹ Potential COVID-19 Illness Visit
Visit description	Screening at ≤28 d pre-V1	Pre-dose	Dose 1 (D1)	3 d post-D1	7 d post-D1	28 d post-D1	3 m FU post-D1	6 m FU post-D1	Dose 2 (6 to 7 m post-D1)	7 d post-D2	28 d post-D2	3 m FU post-D2	6 m FU post-D2		
Days relative to Dose 1	N/A	1	1	3	8	29	90	180						N/A	N/A
Permitted visit window				+2 d	+2 d	±3 d	±7 d	-10 d to +30 d	+30 d post-V6	+2 d from 7 d post-D2	±3 d from 28 d post-D2	±7 d from 3 m post-D2	±10 d from 6 m post-D2		
Maximum total blood volume (mL) drawn per visit	25	175	0	15	170	155	155	155		170	155	155	155	155	65

- a. Brief (symptom-directed) physical examination as indicated.
- b. At 1 h (±15 minutes) before and after dosing.
- c. Vital signs: systolic/diastolic blood pressure, pulse rate, respiratory rate, and oral body temperature.
- d. Dipstick urine analysis: For details of all assessed urine clinical laboratory parameters, see Section 10.3.
- e. Viral screen: screen for human immunodeficiency virus (HIV)-1 and HIV-2, Hepatitis B, and Hepatitis C.
- f. Clinical laboratory tests: Chemistry and hematology. Only in women who are not VOCBP (to confirm postmenopausal status): follicle stimulating hormone at Visit 0. Only for VOCBP: serum β-HCG at Visit 0. For details of all assessed blood clinical laboratory parameters, see Section 10.3.

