- Any case of myocarditis or pericarditis documented within 28 d after BNT162b4 + BNT162b2 Bivalent, BNT162b4 + BNT162b2 Monovalent (OMI XBB.1.5), or BNT162b4 alone administration with ECG or clinical laboratory findings supporting probable or possible myocarditis or pericarditis as per Brighton Collaboration Case Definition (see Section 8.3.8).

NOTE:

- Reactogenicity e-diary data confirmed by the investigator as being entered by the subject in error will not contribute toward a pausing rule.
- Data from recipients of BNT162b2 Bivalent alone will not support the pausing rules.

7.1.2 *Individual trial subject trial treatment pausing rules*

Trial treatment administration for an individual trial subject will be paused (if applicable), pending IRC review, if any of the below criteria are met:

- Safety concerns are identified by an investigator or the IRC.
- Permanent discontinuation (stopping) of trial treatment.

Trial treatment administration will be permanently discontinued for an individual trial subject if any of the below criteria are met.

- Any Grade 4 reactogenicity event considered to be related.
- Pregnancy.
- If a subject's trial treatment assignment is unblinded prior to Visit 5.

After pausing trial treatment according to Sections 7.1.1 or 7.1.2, the IRC may recommend a permanent discontinuation of trial treatment overall, in a cohort, or just for a single trial subject.

A permanent discontinuation of trial treatment may also occur for non-medical reasons at the judgment of the investigator or the subject (i.e., subject moves to a new location).

Trial subjects permanently discontinued from trial treatment will not be discontinued from the trial (i.e., will continue with trial visits and be evaluated for safety). The only exception is pregnant women who will not have further blood draws, but will otherwise complete all

planned assessments, if required including pregnancy follow-up as described in Section 10.5.3.

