#### Safety Set

All participants who received at least one dose of IMP.

Analyses of all safety endpoints will be performed using the Safety Set, based on the treatment and dose the participants actually received. The analyses of data post-Dose 1 will be based on the Safety Set.

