#### Dose 2 Safety Set

All participants who received two doses of IMP.

Analyses of safety endpoints will be performed using the Dose 2 Safety Set as appropriate, based on the dose the participants actually received. The analyses of data post-Dose 2 will be based on the Dose 2 Safety Set.

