The number and percentage of participants reporting local reactions up to seven days after each IMP dose administration will be summarized by maximum severity and cumulatively across severity levels. This summary will include categories "Any", "Grade 1", "Grade 2", "Grade 3", and "Grade 4". The associated 2-sided Clopper-Pearson 95% CIs will also be displayed.

The Safety Set and Dose 2 Safety Set will be used for post-Dose 1 and post-Dose 2 local reaction summaries respectively. Participants without any reactogenicity data up to seven days after each IMP dose administration will be excluded from the local reaction analysis. Missing values will not be imputed.

In addition, local reactions will also be summarized by:

- Duration (days) of each local reaction after each IMP dose.
- Onset day of each local reaction after each IMP dose.

Bar charts with the proportions of participants for each local reaction up to seven days after each IMP dose administration will be plotted. The bars will be divided into severity categories to highlight the proportions of participants by maximum severity. In addition, a listing of participants in the Safety Set with reported local reactions will be provided.

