### 6.5.1.3 Adverse events

Non-serious AEs will only be collected as of first IMP dose administered while SAEs need to be recorded upon awareness starting once informed consent is given. For Cohorts 1 to 4, AE collection will start from Visit 0 and continue until Visit 4 (i.e., until 1 month follow-up post-Dose 1), and (for participants who consent to a second dose of IMP after issue of

protocol version 5.0) restart from Visit 7 and continue until Visit 9 (i.e., until 1 month follow-up post-Dose 2). For Cohort 5, AE collection will start from Visit 0 and continue until Visit 9 (1 month post-Dose 2). AESIs, SAEs, AEs that lead to trial participant discontinuation or withdrawal, and all AEs linked to confirmed COVID-19 cases will be recorded up to the last planned visit for participants who consent to a second dose of IMP. For participants in Cohorts 1 to 4 completing Dose 1 only, recording will continue until Visit 6 (6 months post-Dose 1). For participants in Cohort 5 completing Dose 1 only, recording will continue until the last scheduled visit (5 months post-Dose 1).

Summary tables will include AEs reported from each IMP administration up to 28 days after each IMP administration, SAEs and AESIs occurring from IMP Dose 1 up to 6 months after each IMP administration for participants in Cohorts 1 to 4 and SAEs occurring from IMP Dose 1 up to 3 months after last IMP administration for participants in Cohort 5. AEs leading to IMP discontinuation or trial withdrawal will be listed, and summarized when at least 10 events in all participants have been reported.

AEs/SAEs post-Dose 1 will be summarized by treatment group post-Dose 1 based on the Safety Set. AEs/SAEs post-Dose 2 will be summarized by treatment group post-Dose 2 based on Dose 2 Safety Set.

All AEs will be coded using the most recent version of the MedDRA® coding system and graded for severity using FDA guidance for “[Toxicity Grading Scale for Healthy Adult and Adolescent Volunteers Enrolled in Preventive Vaccine Clinical Trials](#)”. No imputation for missing grades will be performed.

If an AE is reported more than once for the same participant for a SOC / PT the AE will be counted once for this SOC / PT for the specified reporting period.

All AE (from post-dose) summary tables will be sorted alphabetically by SOC and PT within SOC, unless specified otherwise.

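### In Cohorts 1 to 4, Dose 1 and Dose 2 tolerability are summarised in different people, so a side-by-side reading may partly reflect selection, and no planned table shows how much

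*SAP*

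**What the plan says.** SAP 5.1 assigns the two doses to different sets. For the Safety Set: "The analyses of data post-Dose 1 will be based on the Safety Set". For the Dose 2 Safety Set: "The analyses of data post-Dose 2 will be based on the Dose 2 Safety Set". SAP 6.5.1.1 repeats the split for solicited local reactions: "The Safety Set and Dose 2 Safety Set will be used for post-Dose 1 and post-Dose 2 local reaction summaries respectively". SAP 6.5.1.2 does the same for systemic events. For adverse events, SAP 6.5.1.3 says: "AEs/SAEs post-Dose 2 will be summarized by treatment group post-Dose 2 based on Dose 2 Safety Set".

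The reactogenicity denominators are slightly narrower than the sets: "Participants without any reactogenicity data up to seven days after each IMP dose administration will be excluded from the local reaction analysis".

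Entry to the Dose 2 Safety Set in Cohorts 1 to 4 is conditional:

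- Protocol 1.3: "Visit 7 to Visit 11 only apply for subjects who consent to a second dose of IMP after issue of protocol version 5.0". Footnote a of Protocol Table 2 says the same ("If the subject consents to a second dose of IMP as implemented using protocol version 5.0"). The footnote is attached only to Cohorts 1 and 2, but Protocol 1.3 and 5.1.1.1 apply the consent step to all of Cohorts 1 to 4. Under Protocol Table 3, consent is taken at Visit 5, 6 or 7, well after the Dose 1 reactions.
- Protocol 5.1.1.1 also requires prior BNT162b4 and a judgment by the investigator that the person is healthy.
- Protocol 7.1.2 permanently ends trial treatment for a person with the following: "Any Grade 4 reactogenicity event considered to be related".

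Cohort 5 differs: Protocol 8 makes both doses part of the plan for everyone.

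**The concern.** The primary objective for Cohorts 1 to 4 is to describe the safety and tolerability of one and of two doses. Only earlier BNT162b4 recipients receive Dose 2, and they receive it open-label (Protocol 6.3), so there is no concurrent Dose 2 control. The natural reference for Dose 2 is Dose 1, and the treatment-group labels in SAP 6.1 name both doses together.

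As planned, the Dose 1 figures include people who stopped after Dose 1 and the Dose 2 figures do not. If people who tolerated Dose 1 poorly are less likely to return, Dose 2 can look better tolerated without any real change. The routes into Dose 2 act mainly in that direction. I found no planned table of Dose 1 events restricted to Dose 2 recipients, so the report would not show whether this happened.

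**Working it through.** **The plan's own figure.** The only calculable figure is in SAP Table 3: with N=90 and a true rate of 2%, 1 − 0.98^90 = 0.838, stated as 0.84. All 15 cells reproduce. This point does not dispute them. The documents give neither Dose 2 uptake nor reaction rates, so every input below is an assumption.

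**Inputs (assumed).** p = Dose 1 reaction rate. r1 = share of Dose 1 reactors who take Dose 2. r0 = share of non-reactors who do. ρ = within-person correlation between reacting at Dose 1 and at Dose 2. The true Dose 2 rate in the whole group is also set to p (no real change), and uptake depends only on the Dose 1 reaction.

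**Step 1: Dose 1 rate among those who take Dose 2.** q = p·r1 / (p·r1 + (1 − p)·r0).

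| p | r0 | r1 | q |
|---|---|---|---|
| 10% | 0.70 | 0.70 | 10.0% |
| 10% | 0.70 | 0.50 | 0.050/0.680 = 7.4% |
| 10% | 0.70 | 0.35 | 0.035/0.665 = 5.3% |
| 20% | 0.70 | 0.60 | 0.120/0.680 = 17.6% |
| 20% | 0.80 | 0.50 | 0.100/0.740 = 13.5% |
| 20% | 0.80 | 0.40 | 0.080/0.720 = 11.1% |

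With equal uptake, q = p and there is no selection.

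**Step 2: Dose 2 rate among those who take Dose 2.** A Dose 1 reactor reacts again with probability p + ρ(1 − p); a non-reactor reacts with probability p(1 − ρ). Weighting by q and 1 − q gives p − ρ(p − q).

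- Dose 2 minus the full-set Dose 1 column (the plan as written): −ρ(p − q).
- Dose 2 minus the matched Dose 1 column: (1 − ρ)(p − q).

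The true change is zero, so each difference is pure error. For p = 10%, r0 = 0.70, r1 = 0.35, p − q = 4.74 points:

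| ρ | Dose 2 rate in takers | against full-set Dose 1 (10%) | against matched Dose 1 (5.3%) |
|---|---|---|---|
| 0 | 10.0% | 0 | +4.7 points |
| 0.25 | 8.8% | −1.2 | +3.6 |
| 0.5 | 7.6% | −2.4 | +2.4 |
| 1 | 5.3% | −4.7 | 0 |

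At p = 20%, the largest full-set errors (ρ = 1) for the three uptake pairs in Step 1 are −2.4, −6.5 and −8.9 points.

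**Step 3: scale.** In one cohort's vaccine arm of 45, 4.7 points is 0.047 × 45 = 2.1 people. For comparison, the Clopper-Pearson 95% interval for 4 of 45 runs from 2.5% to 21.2%.

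**The case against.** The strongest reply is that the SAP makes no Dose 1 to Dose 2 comparison. The estimands are frequencies after every dose, no hypotheses are tested (SAP 2), and people who received Dose 2 are the right denominator for a post-Dose 2 frequency. That stands: nothing in the planned tables is wrong. What is missing is a companion summary, because columns by dose will be read together in a trial whose primary aim is description.

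The SAP also offers partial protection. SAP 6.2 counts who was eligible for and who received Dose 2, and gives reasons for discontinuation. SAP 6.3.1 shows demographics for the Dose 2 Safety Set. The listings hold each person's reactions. None of these gives Dose 1 tolerability as a rate by Dose 2 uptake.

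The matched column is not a clean answer either. It restricts Dose 1 to people chosen partly on their Dose 1 result, so Dose 2 regresses to the mean. At ρ = 0 the plan as written is correct (10% against 10%), while the matched pair shows a false near-doubling (5.3% against 10%). At ρ = 0.5 the two errors are equal in size. This stands and shapes the fix.

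Finally, the only rule explicitly tied to a solicited-reaction grade concerns related Grade 4 events. It does not establish that uptake is halved after ordinary severe reactions. This also stands: the differential uptake above is illustrative.

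**Conclusion.** The gap is real but modest. In Cohorts 1 to 4 the two doses are described in different people, the second group is selected by consent and health, and no planned summary shows the consequence. Any apparent change from Dose 1 to Dose 2 may be partly selection. In the illustrations the error in the planned reading runs from 0 to 4.7 points at a 10% Dose 1 rate and from 0 to 8.9 points at 20%. The upper ends require both the assumed uptake gap and the same people reacting at both doses.

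Three stronger readings are tempting and the documents do not support them.

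- A reader might infer that a fall from Dose 1 to Dose 2 is selection. No uptake or tolerability data are given, and the effect is zero if uptake is unrelated to Dose 1 reactions.
- A reader might infer that an unchanged pattern would show as a fall from 10% to about 5%. That is the extreme case ρ = 1.
- A reader might extend the point to Cohort 5. There both doses are planned for all, so only dropout or the criteria for withholding Dose 2 can select.

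Selection is also not the only confounder. Dose 2 is open-label, comes 6 to 7 months later, and carries a different spike component in Cohorts 3 and 4.

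**What to change.** In SAP 6.5.1.1 to 6.5.1.3, keep every planned table and add for Cohorts 1 to 4:

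1. Post-Dose 1 reactogenicity and adverse-event summaries in the Dose 2 Safety Set, by treatment group, beside the existing columns.
2. Dose 1 maximum grade by whether Dose 2 was received, among BNT162b4 recipients. This shows directly whether uptake was related to tolerability.
3. Ideally, a within-person cross-table of Dose 1 by Dose 2 maximum grade, which shows how strongly reactions repeat.

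Do not name the matched pairing as the sole basis for statements about Dose 1 and Dose 2. Show both Dose 1 columns, with a note that the full-set column is open to selection, that the matched column is open to regression to the mean, and that Dose 2 is open-label with a different spike component in Cohorts 3 and 4.

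Two passages should be reconciled at the same time. Protocol 9.4.2 bases all safety analyses on the Safety Set, while SAP 8.1 records no change to the protocol-planned analyses. SAP Table 7 marks Cohort 1 as dosed once, while SAP Table 1 lists a Dose 2 for it; this decides whether Cohort 1 contributes to the added tables.

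This is a cheap improvement. Item 1 reuses an existing analysis set and existing programs. The cost is a few more table pages and the need to carry the caveat.

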#### Immunogenicity Analysis Set

All participants who received the planned dose of the IMP on Day 1 and who have at least one valid immunogenicity assessment within an appropriate window of the target day.

#### Immunogenicity Per Protocol Set

All participants included in the Immunogenicity Analysis Set, that have no major protocol deviations (PDs) that can confound immunogenicity data. A participant will only be excluded from the Immunogenicity Per Protocol Set if the participant had an important protocol deviation that can confound all immunogenicity data as determined by the sponsor. If a participant has an important protocol deviation that can confound subsequent immunogenicity data as determined by the sponsor then the participant will remain in the Immunogenicity Per Protocol Set, and only samples before the event will be included in the analysis.

Participants who have positive central or local nucleic acid amplification-based test (NAAT) result at pre-Dose 1 will be excluded from Immunogenicity Per Protocol Set since active infection indicated by positive NAAT at pre-Dose 1 may impact immunogenicity assessments post dose even though this is not a protocol deviation.

For immunogenicity analyses, the sampling windows with grace periods specified in [Table 4](#) will be used to define the valid samples for analysis sets. The samples drawn within the visit specific window with grace period will be valid for immunogenicity analysis in both the Immunogenicity Analysis Set and the Immunogenicity Per Protocol Set. Immunogenicity Per Protocol Set will be used for secondary and [CCI](#) endpoints in the BNT162-21 trial. Immunogenicity Analysis Set will not be used for immunogenicity analyses as the analyses based on Immunogenicity Per Protocol Set will serve the objectives of the study.

Only participants without breakthrough SARS-CoV-2 infections (without positive central or local NAAT results from pre-Dose 1 through the visit) will be analyzed for the respective visit.

**Table 4: Immunogenicity sampling window**

Visit relative to dose	Window per CTP	Additional grace period = No impact on immunogenicity Include in Immunogenicity Analysis Set and Immunogenicity Per Protocol Set	Impact on immunogenicity = Exclude from Immunogenicity Analysis Set and Immunogenicity Per Protocol Set, only for primary endpoints
Day 7 post-dose	8+2 8-10 days	N/A	All OOW
Day 28 post-dose	29±2 27-31 days	+/- 2 days OOW ≥25 to ≤33 days	≥+/- 3 and more days OOW <25 days or >33 days
Month 3 post-dose	90±7 83-97 days	+/- 7 days OOW ≥76 to ≤104 days	≥+/- 8 and more days OOW <76 days or >104 days
Month 6 post-dose*	180±10 170-190 days	+/- 7 days OOW ≥163 to ≤197 days	≥+/- 8 and more days OOW <163 days or >197 days

**Abbreviations:** N/A = Not Applicable; OOW= Out of Window.

\*Participants who received a pre-Dose 2 blood draw will be reported at this timepoint regardless of window as Month 6 post-Dose 1/Pre-Dose 2.

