- g. In VOCBP: The serum β-HCG pregnancy test at Visit 0 will be performed using the sample collected for clinical laboratory tests. Before each dosing, urine pregnancy tests will be performed using a commercial kit at the site and the trial subjects will be counseled about the need for consistent and correct use of a highly effective method of contraception.
- h. Leftover blood after completion of the assessments may be used for additional biomarker analyses and/or development of analytical methods.
- i. Trial site personnel will remind the subjects to record the oral body temperature and the worst grade for each symptom in the e-diary at approximately the same time every evening on the day of IMP administration and then every day in the evening for a total of seven consecutive days. Ask/remind the subject to contact the site if they experience any severe or potentially life-threatening reactogenicity events. Trial site personnel will remind the subjects to record the use of antipyretic/analgesic medication to treat symptoms associated with IMP administration for 7 d after each IMP dose using the e-diary.
- j. Only SAEs, adverse event(s) of special interest, AEs that lead to discontinuation or withdrawal, and AEs linked to confirmed COVID-19 cases will be recorded. SAEs must be recorded upon awareness.
- k. For FU visits, only any prohibited medication (including SARS-CoV-2 non-trial vaccinations) will be recorded.
- l. Optimally within 3 d after potential COVID-19 illness onset. All known NAAT-based SARS-CoV-2 positive subjects, from randomization until end of trial, will be asked for an additional unscheduled visit to define the COVID-19 illness as per Section 8.2.8. The COVID-19 illness visit will define the illness as either confirmed COVID-19, unconfirmed COVID-19, or confirmed severe COVID-19.
- m. The results must be available prior to administration of trial treatment at Visit 1.
- n. Blood samples for CCI assessment at "Potential COVID-19 Illness Visit" should only be collected if the visit occurs more than 2 months after the last IMP dose.
- o. This visit will apply to sentinel subjects only.
- p. Visit 6 and Visit 7 can (should ideally) occur on the same day.

- q. Informed consent can be obtained for Dose 2 at either Visit 5, 6 or Visit 7.
- r. Only for subjects that received BNT162b2 Bivalent + BNT162b4 for Dose 1 and who consented to a second (Dose 2).
- s. To be completed before administration of Dose 2.

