9.3 Analysis sets

The following analyses sets are defined:

Analysis set	Description
Screened Set	All subjects who provided informed consent.
Safety Set	All subjects who received at least one dose of IMP.
Dose 2 Safety Set	All subjects who received two doses of IMP.
Randomized/Assigned Set	All subjects who were randomized/assigned with a subject number using the online randomization tool.
Immunogenicity Analysis Set	All subjects who received the planned dose of the IMP on Day 1 and who have at least one valid viral neutralization titer assessment within an appropriate window of the target day.
Immunogenicity Per Protocol Set	All subjects included in the Immunogenicity Analysis Set that have no major protocol deviations that can confound immunogenicity data.

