**6.6 Immunogenicity analyses**

The neutralizing antibody titers above the lower limit of quantitation (LLOQ) are considered accurate and their quantitated values will be reported. Neutralizing antibody titers below the LLOQ will be set to  $0.5 \times$  LLOQ for all the analysis if not specified otherwise. Missing data will not be imputed.

Only participants without breakthrough SARS-CoV-2 infections (without positive central or local NAAT from pre-Dose 1 through the visit) will be analyzed for the respective visit.

The number of participants with blood samples drawn at each visit and their respective time windows as specified in [Table 4](#) will be summarized for the Safety Set.

[Table 7](#) and [Table 8](#) below lists the neutralizing antibody titer assay results to be assessed for each variant strains at specific visit for Cohorts 1 to 5.

**Table 7: Humoral immune response analysis against variants at selected timepoints for Cohorts 1 – 4 in the final study report**

	Cohort 1 (≥18-55 yoa) N=45 BNT162b2 + 5ug BNT162b4 - once N=15 BNT162b2	Cohort 2 (≥18-55 yoa) N=45 BNT162b2 + 10ug BNT162b4 - twice N=15 BNT162b2	Cohort 3a (≥18-55 yoa) N=45 BNT162b2 + 15ug BNT162b4 - 2nd dose XBB1.5 N=15 BNT162b2	Cohort 3b N=45 BNT162b2 + 15ug BNT162b4 - 2nd dose XBB1.5 N=15 BNT162b2	Cohort 4a (≥18-55 yoa) N=45 BNT162b2 + 30ug BNT162b4 - 2nd dose XBB1.5 N=15 BNT162b2	Cohort 4b N=45 BNT162b2 + 30ug BNT162b4 - 2nd dose XBB1.5 N=15 BNT162b2
V1 – Baseline (Pre-Dose 1)	WT, BA.4/5	WT, BA.4/5	WT, BA.4/5	WT, BA.4/5	WT, BA.4/5	WT, BA.4/5
V4 – Day 28 post-Dose 1	WT, BA.4/5	WT, BA.4/5	WT, BA.4/5	WT, BA.4/5	WT, BA.4/5	WT, BA.4/5
V6 – Month 6 post-Dose 1; pre-Dose 2	WT, BA.4/5	WT, BA.4/5	WT, BA.4/5, and XBB.1.5	WT, BA.4/5, and XBB.1.5	WT, BA.4/5, and XBB.1.5	WT, BA.4/5, and XBB.1.5
V9 – Day 28 post-Dose 2	NA	WT, BA.4/5	WT, XBB.1.5	WT, XBB.1.5	WT, XBB.1.5	WT, XBB.1.5

WT: Ancestral strain. NA: Not applicable.

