- h. Leftover blood after completion of the assessments may be used for additional biomarker analyses and/or development of analytical methods.
- i. Trial site personnel will remind the participants to record the oral body temperature and the worst grade for each symptom in the e-diary at approximately the same time every evening on the day of IMP administration and then every day in the evening for a total of seven consecutive days. Ask/remind the subject to contact the site if they experience any severe or potentially life-threatening reactogenicity events. Trial site personnel will remind the participants to record the use of antipyretic/analgesic medication to treat symptoms associated with IMP administration for 7 d after each IMP dose using the e-diary.
- j. For FU visits, only adverse event(s) of special interest, any SAEs, and all AEs linked to confirmed COVID-19 cases will be recorded. SAEs must be recorded upon awareness.

- k. For FU visits, only any prohibited medication (including SARS-CoV-2 non-trial vaccinations) will be recorded.
- l. Optimally within 3 d after potential COVID-19 illness onset. All known NAAT-based SARS-CoV-2 positive participants, from randomization until end of trial, will be asked for an additional unscheduled visit to define the COVID-19 illness as per Section 8.2.8 of protocol. The COVID-19 illness visit will define the illness as either confirmed COVID-19, unconfirmed COVID-19, or confirmed severe COVID-19.
- m. The results must be available prior to administration of trial treatment at Visit 1. If the initial N-binding antibody test is negative, this test needs to be repeated if performed >28 d prior to the planned vaccination.
- n. Blood samples for **CCI** assessment at "Potential COVID-19 Illness Visit" should only be collected if the visit occurs more than 2 months after the last IMP dose.
- o. This visit will apply to sentinel participants only.
- p. Visit 6 and Visit 7 can (should ideally) occur on the same day.
- q. Informed consent can be obtained for Dose 2 at either Visit 5, 6 or Visit 7.
- r. Only for participants that received BNT162b2 Bivalent + BNT162b4 for Dose 1 and who consented to a second (Dose 2).
- s. To be completed before administration of Dose 2.
- t. The assessment/sampling at Visit 7 will only be performed if not done at Visit 6.
- u. Not for Cohorts 4a and 4b.

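### SAP Table 4 gives the Month 6 post-Dose 1 window as 180±10 days where the protocol allows −10/+30 days, and its exemption for late samples is not open to controls

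*SAP*

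**What the plan says.** SAP Table 4 has a single Month 6 row covering both doses. The column for the protocol window reads "180±10 170-190 days". A 7-day grace period extends this to Days 163-197, and the last column marks anything outside that range for exclusion.

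The schedule of activities (Protocol 1.3, Table 3) has two Month 6 visits with different windows. V6, at Day 180 after Dose 1, may be 10 days early to 30 days late. V11 is ±"10 d from 6 m post-D2". SAP Appendix 4, Table 10 repeats the asymmetric V6 window.

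Protocol 9.3 does not fix an analysis window; it asks for "at least one valid viral neutralization titer assessment within an appropriate window of the target day". SAP 5.1 fills the gap by reference to Table 4: "The samples drawn within the visit specific window with grace period will be valid for immunogenicity analysis".

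The Table 4 footnote makes one exception: "Participants who received a pre-Dose 2 blood draw will be reported at this timepoint regardless of window as Month 6 post-Dose 1/Pre-Dose 2". Footnote r to the protocol schedule restricts the second injection: "Only for subjects that received BNT162b2 Bivalent + BNT162b4 for Dose 1 and who consented to a second (Dose 2". Inclusion criterion 17 and Protocol 6.3 say the same. Footnote t to SAP Table 10 adds that "The assessment/sampling at Visit 7 will only be performed if not done at Visit 6".

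SAP Table 7 plans titers at "V6 – Month 6 post-Dose 1; pre-Dose 2" for every cohort, and each column heading includes 15 BNT162b2 controls.

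**The concern.** A SAP may set an analysis window narrower than the visit window, and Protocol 9.3 leaves room for that. Table 4 does not present its figure as such a choice. It presents ±10 days as the protocol's own window, which is wrong for V6 and contradicts the SAP's own schedule.

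The footnote then makes the limit depend on Dose 2 status. SAP footnote t allows the V6 draw itself to serve as the pre-Dose 2 draw. A V6 sample on Day 205 would therefore be kept for a BNT162b4 recipient who goes on to Dose 2, and would not be valid for a control bled on the same day. At stake is whether the Month 6 titers shown by treatment group rest on the same sampling rule in every group.

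There is also a labelling problem. SAP 6.6 calls for a Safety Set summary of samples by Table 4 window, and SAP 6.6.1.3 for a listing with a window indicator. The summary would report compliant V6 samples as out of window, and so would the listing if its indicator is built on Table 4.

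**Working it through.** **Inputs.** Table 4, Month 6: target Day 180, ±10 days, grace ±7 days. Protocol Table 3 and SAP Table 10, V6: Day 180, −10 to +30 days. Protocol Table 3, V11: ±10 days. Controls per cohort (Protocol Table 2, SAP Table 1): 2 + 13 = 15 in Cohorts 1, 2, 3a and 4a; 15 in each of 3b and 4b. Day 1 is the day of dosing.

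**1. Reproduce Table 4.** 180 − 10 = 170 and 180 + 10 = 190. With grace, 170 − 7 = 163 and 190 + 7 = 197. The row is consistent within itself.

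**2. Compare it with the protocol.** V11: 170-190, which agrees. V6: 180 − 10 = 170 and 180 + 30 = 210, which does not. Table 4 has carried the post-Dose 2 window into a row that also serves post-Dose 1.

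**3. Count the V6 days affected.**

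| V6 days | Number | Share of permitted days | Status under Table 4 |
|---|---|---|---|
| 170-210 | 210 − 170 + 1 = 41 | 100% | All allowed by the protocol |
| 191-210 | 20 | 20/41 = 48.8% | Labelled out of window |
| 191-197 | 7 | 7/41 = 17.1% | Recovered by grace |
| 198-210 | 20 − 7 = 13 | 13/41 = 31.7% | Not valid without a pre-Dose 2 draw |

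These are shares of calendar days, not of samples. In the Day 205 example, 205 − 190 = 15 days, beyond the 7 days of grace.

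**4. Count who is under the narrower limit.** All controls: 6 × 15 = 90. Aged 18-55 (Cohorts 1, 2, 3a, 4a): 4 × 15 = 60. Aged over 55 (3b, 4b): 2 × 15 = 30. These are the three control columns in SAP 6.1, each affected in full. BNT162b4 recipients who do not go on to Dose 2 are under the same limit; their number is not given.

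**5. Check the correction.** With the V6 window at 170-210 and the same grace, the limits become 163-217 (55 days, against 197 − 163 + 1 = 35 now), and no compliant V6 day is lost.

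**6. Check the Day 28 row.** Table 4 labels it 29±2; the protocol allows ±3, that is Days 26-32. Table 4 accepts Days 25-33, so no compliant sample is lost. This one is editorial.

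**The case against.** The strongest counter-argument is that Table 4 may exclude no titer at all. Its exclusion column is limited by its heading to the primary endpoints, and SAP 6.5 says these are safety endpoints. SAP 5.1 says in-window samples are valid but gives no separate instruction to drop the others, and SAP 6.1.3 assigns visits from the EDC record. This shows a real ambiguity. It does not remove the problem: SAP 5.1 still makes Table 4 the definition of a valid sample, visit assignment is a different question from validity, and compliant samples are mislabelled on either reading.

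Second, a pre-Dose 2 draw is not defined, and Table 7 attaches that label to the V6 timepoint in columns that include controls. A reading that exempts every V6 draw is possible but less natural, since controls have no Dose 2. If that was the intention, the SAP should say so.

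Third, footnote t differs between the documents. The protocol's version lets sampling be done once when Visits 6 and 7 are combined, which suggests that separate visits might each be sampled; the exempt draw would then be the one at V7. The Day 205 example holds for combined visits, which the protocol calls ideal; for separate visits it depends on which footnote governs.

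Fourth, the difference follows Dose 2 status rather than arm as such. Table 7 also describes Cohort 1 as dosed once; on that reading the cohort has no difference between arms, although SAP Table 1 and SAP 6.1 list a Dose 2 for it.

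Finally, limits of 163-217 would put titers up to 217 − 163 = 54 days apart under one label. That is a fair reason to consider a tighter window, provided it is stated as the SAP's own and applied to all arms. The current footnote already admits late draws without limit for Dose 2 recipients.

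**Conclusion.** The concern holds, at minor severity. The Month 6 entry is wrong as a statement of the protocol's V6 window. If SAP 5.1 governs, and if the footnote means a draw before a Dose 2 that is actually given, compliant V6 samples on 13 of 41 permitted days are not valid for any of the 90 planned controls or for BNT162b4 recipients who stop after Dose 1, while they are kept for those who proceed. Whichever way the exclusion heading is read, 20 of the 41 days are mislabelled.

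The number of samples affected is not in the documents and may be zero, and the direction of any bias is unknown. The Day 28 secondary endpoints are unaffected, and the footnote protects the XBB.1.5 value used as the Dose 2 baseline. No formal comparison between dose levels is planned. The planned window summary and assay listing would make late samples visible, though wrongly labelled.

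**What to change.** - Split the Month 6 row in SAP Table 4. Post-Dose 1: 180 −10/+30 (Days 170-210; 163-217 if the 7-day grace is kept). Post-Dose 2: 180±10, unchanged.
- Apply the same post-Dose 1 limit to all arms wherever Month 6 post-Dose 1 results are shown by treatment group.
- Keep pre-Dose 2 draws outside that limit as the Dose 2 baseline. If they also appear at the combined Month 6/pre-Dose 2 timepoint, flag them.
- In the exclusion column, replace the reference to primary endpoints with the immunogenicity endpoints it covers, so that Table 4 and SAP 5.1 agree.
- Editorial: relabel Day 28 as 29±3 (Days 26-32). The accepted limits of 25-33 can stay, as 1 day of grace.

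The cost is SAP wording, a revised Month 6 window flag, and a flag or footnote in the Month 6 output. No new data are required.
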